4.1.3 Method of assigning patients to treatment groups

An Interactive Response Technology (IRT) system will be used in this trial in order to dispense medication kits as well as manage initial/re-supply ordering of medication kits. The study site will be required to complete the appropriate module within the IRT system.

The investigator will receive all necessary instructions to access the IRT system from the Sponsor or chosen provider. Detailed IRT transactions and procedures will be documented in the user requirement specifications mutually agreed to by the sponsor and the IRT provider. All medication kit assignments will occur in an open label fashion.

4.1.4 Drug assignment and administration of doses for each patient

Prior to each administration of study drug, a urine pregnancy test will be performed on site. If this test has a positive result, the administration of study drug should not proceed and this urine test should be confirmed by a serum pregnancy test.

A total dose of 600 mg of BI 655130 will be administered to each patient every 4 weeks starting with Visit 1 until the End of Treatment (Week 204). IRT will dispense 4 medication kits at each drug administration. Each kit will contain one syringe. Each patient will receive all 4 syringes (4 injections) of study drug. Each of the four 1mL prefilled syringes will contain 150mg/mL of BI 655130 for a total dose of 600mg.

Study drug will be administered exclusively at the study site by a Health Care Professional (HCP) which will be the investigator or other authorized study personnel (e.g. study nurse). Study drug will be administered as a SC injection in the abdomen or thighs. Injections being given in the same area should be at least 2 cm apart and should not be close to a vein. The injection site should avoid sites where the skin is tender, bruised, erythematous, or indurated, and should be alternated to other areas for subsequent doses.

Dose modifications or adjustments are not permitted.

Interruption of trial treatment may be needed to treat AEs (ie. Infections) and trial treatment should be restarted as soon as medically justified. See [Section 4.2.1](#).

Refer to [Section 6.2.2](#) for rules for dosing limitations within a 14 day period

There are no dietary requirements needed.

In the eCRF, the study drug administration time is always the time of the first injection.

4.1.5 Blinding and procedures for unblinding

4.1.5.1 Blinding

This is an open label trial thus the patient, investigator and everyone involved in the trial conduct or analysis will be aware of the treatment assignment.

The study treatment (BI 655130 or placebo) in which the patient received through Week 16 in the parent trial will be blinded until the database lock (DBL) of the parent trial.

4.1.5.2 Unblinding and breaking the code

Not applicable.

4.1.6 Packaging, labelling, and re-supply

The investigational medicinal products will be provided by Boehringer Ingelheim (BI) or a designated Clinical Research Organization (CRO). They will be packaged and labelled in accordance with the principles of Good Manufacturing Practice (GMP). Re-supply to the sites will be managed via an IRT system, which will also monitor expiry dates of supplies available at the sites. For details of packaging and the description of the label, refer to the ISF.

4.1.7 Storage conditions

Drug supplies will be kept in their original packaging and in a secure limited access storage area according to the recommended storage conditions on the medication label. A temperature log must be maintained for documentation.

Trial medication must be securely stored, e.g. in a locked refrigerator or at a pharmacy. If the storage conditions are found to be outside the specified range, the Clinical Trial Manager (provided in the list of contacts) must be contacted immediately. Refer to the storage conditions for trial medications (STORM) document in the ISF for additional information.

The medication may only be dispensed to trial patients according to the Clinical Trial Protocol (CTP) by authorized personnel as documented in the trial staff list.

4.1.8 Drug accountability

The investigator or designee will receive the investigational drugs delivered by the sponsor when the following requirements are fulfilled:

- Approval of the clinical trial protocol by the IRB / ethics committee (EC)
- Availability of a signed and dated clinical trial contract between the sponsor and the investigational site,
- Approval/notification of the regulatory authority, e.g. competent authority,
- Availability of the curriculum vitae of the Principal Investigator,
- Availability of a signed and dated clinical trial protocol,
- Availability of the proof of a medical license for the Principal Investigator (if applicable)
- Availability of FDA Form 1572 (if applicable).

Investigational drugs are not allowed to be used outside the context of this protocol. They must not be forwarded to other investigators or clinics unless there is Sponsor approval. All patients will be dosed in the clinic and will not be taking investigational product home. The investigator or designee must maintain records of the product's delivery to the trial site, the inventory at the site, the use by each patient, and the return to the sponsor or warehouse / drug distribution centre or alternative disposal site of unused products. If applicable, the sponsor or warehouse / drug distribution centre will maintain records of the disposal.

These records will include dates, quantities, batch / serial numbers, expiry ('use- by') dates, and the unique code numbers assigned to the investigational medicinal product and trial patients. The investigator or designee will maintain records that document adequately that the patients were provided the doses specified by the Clinical Trial Protocol (CTP) and reconcile all investigational medicinal products received from the sponsor. At the time of return to the sponsor and/or appointed CRO, the investigator or designee must verify that all unused drug supplies have been returned by the clinical site staff and all used or partially used drug supplies have been destroyed on site and that no remaining supplies are in the investigator's possession.

4.2 OTHER TREATMENTS, EMERGENCY PROCEDURES, RESTRICTIONS

4.2.1 Other treatments and emergency procedures

Stable doses of concomitant therapies for chronic conditions, for which neither the condition nor the treatment are judged to exclude the patient from participation are permissible. All concomitant medications should be carefully evaluated by the investigator and the Clinical Trial Manager should be contacted when there are questions regarding concomitant medications.

During the trial, if the severity and progression of the patients' AD worsens the investigator can treat the patient with rescue treatment i.e. Standard of Care (SoC) of his/her choice. The sponsor will not provide/supply SoC treatment(s) to the sites. Refer also to [Section 4.2.2.1](#).

Patients with active systemic infections during the parent 655130 study must delay Visit 1 in this study until the infection has resolved for at least 2 weeks.

Severe infections according to Rheumatology Common Toxicity Criteria (RCTC) grading, serious infections, and opportunistic or mycobacterium tuberculosis infections:

Treatment of the infection should be initiated promptly according to local SoC. No further trial medication should be administered until the active infection has resolved.

Treatment with BI 655130 may be restarted when the patient has recovered according to investigator's assessment.

Malignancies

In case of occurrence of malignant neoplasm other than appropriately treated basal cell carcinoma or squamous cell carcinoma of the skin or in situ carcinoma of uterine cervix, the investigator should discontinue treatment with the trial medication, and notify the Clinical Trial Manager (CT Manager). Diagnostics and treatment should be initiated according to local SoC.

Systemic Hypersensitivity including anaphylactic reaction

In case of systemic hypersensitivity including anaphylactic reaction emerging during or after injection(s) of trial medication, the investigator should consider in accordance with severity of the reaction and local SoC to

1. Stop further injection(s)
2. Treat with systemic anti-histamines, i.v. steroids, and in case of a severe allergic reaction (e.g., anaphylactic reaction) epinephrine

Also draw a plasma sample for IgE and Antidrug antibodies (ADA) as detailed in the laboratory manual and consider the evaluation of histamine, serum tryptase, and complement components.

In case of systemic hypersensitivity, based on patient's clinical course and medical judgment, injections may be cautiously re-initiated or continued in case of mild or moderate systemic hypersensitivity (according to RCTC grading, provided in the ISF).

In case of anaphylactic reaction based on the criteria discussed in the statement paper from Sampson HA ([Appendix 10.1, R11-4890](#)) suspected to be caused by the trial medication, the investigator should discontinue treatment with study drug.

In case of potential systemic allergic reaction, blood samples for determination of serum tryptase will be collected 0.5 h, 2 h, 6 h, and 24 h after onset of the event.

There are no special emergency procedures to be followed.

4.2.2 Restrictions

4.2.2.1 Restrictions regarding concomitant treatment

The medication (or classes of medications) listed in [Table 4.2.2.1:1](#) are restricted for the entire study participation (V1 through to EOS). In the event that EOS/V1 cannot be done on the same day and a gap is needed from EOS of the 1368-0032 to visit 1 of this trial, restricted medication allowed and washout periods are noted in the right column of table.

Table 4.2.2.1: 1 Restricted Medications

Medication or class of medications during study ¹	Washout periods prior to V1
Dupilumab, UVB phototherapy, PUVA	Not allowed during gap
Hydroxyzine, diphenhydramine, doxepin	Must be stopped 1 week before Visit 1
Any other topical medication particularly moisturizers containing urea or high potency topical steroids ³	Must be stopped at Visit 1
Methotrexate, cyclosporine, retinoids, azathioprine	Must be stopped 4 weeks prior to Visit 1
IL36R inhibitors	Not allowed during gap
All other biologics, including but not limited to etanercept (Enbrel®), adalimumab (Humira®), infliximab (Remicade®), ustekinumab (Stelara®), secukinumab (Cosentyx®), brodalumab (Siliq®), guselkumab (Tremfya®), ixekizumab (Taltz®), tildrakizumab (Ilumya®), risankizumab (Skyrizi®), rituximab,	Not allowed during gap
live virus vaccinations	Not allowed during gap
other systemic immunomodulating treatments (e.g. corticosteroids ² , cyclophosphamide), tofacitinib (Xeljanz®), apremilast (Otezla®)	Must be stopped 4 weeks prior to Visit 1
Any investigational device or product	Not allowed during gap

¹ In case of worsening of the AD in the treatment period the use of a rescue medication is left at the discretion of the investigator.

²No restriction on inhaled corticosteroids to treat asthma or corticosteroid drops administered in the eye or ear.

³Low potency topical steroids and non-urea containing moisturizers are allowed.

Restricted medication is defined as the use of any drugs listed in the [Table 4.2.2.1:1](#) for any reason with the exception of unstable or worsening of AD). If the restricted medication is taken during the trial, trial treatment discontinuation is not mandatory. The continuation of the treatment is left at the discretion of the investigator.

Rescue medication is defined as the use of highly potent topical corticosteroids, systemic immunomodulating treatments or biologics for the treatment of unstable or worsening of AD. The use of the rescue medication leads to the discontinuation of the trial treatment.

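### Some therapies for worsening AD are neither clearly restricted nor rescue, and the non-responder rule keys on drug discontinuation, so a flare-treated patient can count as a Week-48 responder

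*Protocol*

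**What the plan says.** Protocol 4.2.2.1 works with two classes of therapy.

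- *Rescue* is "defined as the use of highly potent topical corticosteroids, systemic immunomodulating treatments or biologics for the treatment of unstable or worsening of AD". Its consequence is fixed: "The use of the rescue medication leads to the discontinuation of the trial treatment". Protocol 3.3.4.1 repeats the stop and points back to 4.2.2.1.
- *Restricted medication* is anything in Table 4.2.2.1:1 used "for any reason with the exception of unstable or worsening of AD". Its consequence is soft: "If the restricted medication is taken during the trial, trial treatment discontinuation is not mandatory". One table row reads "Dupilumab, UVB phototherapy, PUVA"; another covers any other topical medication, and footnote 3 frees only low-potency steroids and moisturisers without urea. The opening sentence of the section restricts every listed item from Visit 1 to end of study, with no exception for flares.

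Two further statements deal with flares. Footnote 1 to the table says: "In case of worsening of the AD in the treatment period the use of a rescue medication is left at the discretion of the investigator". Protocol 4.2.1 says that, when AD worsens, "the investigator can treat the patient with rescue treatment i.e. Standard of Care (SoC) of his/her choice".

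On the analysis side, SAP 6.6.2 rule 1 treats binary data as missing once study medication is stopped early, with a cut-off at the last dose plus 4 weeks (including the extended windows). A missing result becomes non-response unless both neighbouring visits are responses. Continuous endpoints use observed data. Neither SAP 6.6.2 nor Protocol 7.3 has a rule that uses the start of rescue or other AD therapy.

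**The concern.** Flares that need treatment are foreseeable here. Protocol 1.4.2 warns that some patients may lose response because exposure is lower than in the parent trial, and 4.1.2 puts a 600 mg SC dose at about 60% of the exposure of the IV dose.

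If the class of a flare therapy is unclear, two sites can both follow the protocol and treat the same flare differently. One stops trial drug, and the patient becomes a non-responder. The other continues drug, and the patient may be a responder. There is no control arm, so clearance helped by phototherapy or an active topical would be read as an effect of BI 655130. In the analysis from the parent-trial baseline it would look like maintained response. Status reviews of these data may support regulatory submissions (Protocol 7.2.7).

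**Working it through.** The plan states no response rate, sample size calculation or power for this trial (Protocol 7.1, 7.5), so there is no figure to reproduce. The check is a comparison of texts, then simple arithmetic.

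**1. How the protocol classes the therapy.** Take UVB, a mid-potency topical steroid or a non-steroid anti-inflammatory topical, given for worsening AD.

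| Reading | Text behind it | Trial drug | Week-48 binary result under SAP 6.6.2 |
|---|---|---|---|
| Neither class | The restricted definition excepts flare use; the rescue list does not name the therapy | May continue | Observed result counts |
| Restricted | Opening sentence of 4.2.2.1 | Stopping not mandatory | Observed result counts, unless the patient cannot give the therapy up and is stopped under 3.3.4.1 |
| Rescue | 4.2.1 and table footnote 1 | Must stop | Missing after last dose + 4 weeks, then non-response |

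PUVA is less clear. It could be called a systemic immunomodulating treatment, but the table places it in a different row from that group. Highly potent topical steroids do not belong in this comparison, because the rescue definition names them.

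**2. Listed rescue and the cut-off.** Inputs from SAP Table 6.7:1: Week 44 is planned for Day 309, Week 48 for Day 337, and the Week-48 window is Day 324 to 351.

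- Cut-off after a last dose at Week 44: 309 + 28 = Day 337, and later if the extended window is added.
- Day 337 lies inside Day 324 to 351.
- Rescue begun on Day 310 could run for 337 − 310 = 27 days before a Day 337 result that still counts.

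So the gap in timing also reaches therapy that is rescue by definition and does stop the drug.

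**3. Size.** Let k be the patients who count as Week-48 responders under the current rule although rescue or flare therapy began before that result. Scoring them as non-responders lowers the rate by k/N. N is about 40 and at most 45 (Protocol 7.5). The documents do not give k.

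| k (assumed) | N = 40 | N = 45 |
|---|---|---|
| 0 | 0 | 0 |
| 1 | 1/40 = 2.5 points | 1/45 = 2.2 points |
| 2 | 2/40 = 5.0 points | 2/45 = 4.4 points |

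If the full analysis set were 30 (assumption), one patient would be 1/30 = 3.3 points.

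For scale, assume 20 of 40 responders: 50.0% (exact 95% limits 33.8 to 66.2). With k = 1 this becomes 19/40 = 47.5% (31.5 to 63.9).

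k/N is what an added run would show. It is an upper bound on the response wrongly credited to the drug, because some of these patients may have responded without the added therapy.

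**The case against.** The case for the plan is fair in several parts.

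- *The text can be read as two tiers.* Section 4.2.1 refers the reader to 4.2.2.1, so the broad phrase there may defer to the rescue list. Potent or systemic therapy then stops drug, and other therapy stops it if the investigator thinks it may interfere (3.3.4.1). That is coherent, but the second tier rests on opinion, and its outcome decides the Week-48 score.
- *UVB is a weak example.* The exception for worsening AD is worded for drugs, and 4.2.2.2 tells patients to avoid prolonged artificial UV light. This makes phototherapy less likely and favours treating it as restricted. It does not touch topicals, and restricted use need not stop drug.
- *There is a deviation route.* Protocol 7.2.1 names use of restricted medication as an important deviation and leaves others to the study team. SAP 6.2 allows decisions on single values, and SAP 7 lists deviations per patient with any exclusion from analysis sets. Flare use is excepted from the restricted definition, though, so mainly the catch-all remains, and the detailed specifications are not visible.
- *Flares are recorded.* Worsening of the underlying disease is an adverse event (5.2.6.1.1), and concomitant and non-drug therapies are tabulated (SAP 7.2). A reader could trace cases by hand, but no visible table links therapy to response.
- *Counting observed response despite minor added therapy is a legitimate choice.* This stands. It is a reason to keep the current analysis and add a second one beside it.

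A reader might infer that every topical above low potency falls in the gap. The documents do not support that: highly potent topical steroids are expressly rescue and must stop drug. Nor do they support a claim that the response rates are inflated by a known amount, since k may be zero.

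**Conclusion.** The point holds within limits. On the wording of 4.2.2.1, UVB (and arguably PUVA), mid-potency topical steroids and non-steroid anti-inflammatory topicals given for worsening AD are neither clearly restricted nor rescue, and 4.2.1 pulls the other way. Because SAP 6.6.2 acts only on discontinuation, such a patient can stay on drug and count as a Week-48 responder. Listed rescue begun after a Week-44 last dose can have the same result.

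The effect is confined to descriptive secondary endpoints (EASI50, EASI75, IGA, with observed EASI and SCORAD also open to it). A reader might infer that the primary endpoint is compromised. It is not: this rule does not enter the count of patients with treatment-emergent adverse events.

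The conclusion rests on the visible text. Parts of the SAP are redacted, and the deviation specifications are held elsewhere. This is a cheap improvement, not a flaw that undermines the trial.

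**What to change.** **SAP 6.6.2.** Add one supplementary non-responder analysis. As its last step, after all current rules, it sets the binary endpoints to non-response from the start date of either:

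- rescue as listed in 4.2.2.1, or
- UVB/PUVA, a mid-potency topical steroid or a non-steroid anti-inflammatory topical given for worsening AD.

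Show it beside the current analysis, which is kept. The two then differ in this step alone. The observed-data tables are not a suitable comparison, because they also differ in how missing and off-drug results are handled.

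**Protocol.** At the next amendment, align 4.2.1 with 4.2.2.1 and its table so that these therapies have a stated class when used for a flare. Leave the rule for highly potent topical steroids unchanged. An amendment needs ethics and authority approval (8.1), so this alone does not justify one.

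**EASI and SCORAD.** A summary that sets aside values after flare therapy is tempting, but it removes flaring patients from observed-case means and may make the results look better. Omit it, or show it only beside the observed-data summary with that warning.

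**Cost.** One extra run and a few lines of text. The response rate in the added run will be slightly lower if k is above zero, and some patients who responded on drug alone after a brief course will be scored as failures. The sponsor must confirm that indication and topical potency are captured; for concomitant therapy, the source list in Protocol 8.3.1 mentions only start date and changes.

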4.2.2.2 Restrictions on diet and life style

There are no restrictions on diet and life style however patients should avoid prolonged exposure to sunlight and artificial UV light.

4.2.2.3 Contraception requirements

Women of childbearing potential (WOCBP) must use highly effective methods of birth control per ICH M3 (R2) that result in a low failure rate of less than 1% per year when used consistently and correctly for the duration of the trial and 16 weeks after the last study drug administration. A list of contraception methods meeting these criteria is also provided in the patient information.

Female Patients:

Acceptable methods of birth control for this trial are:

- Combined (estrogen and progestogen containing) hormonal birth control associated with inhibition of ovulation (oral, intravaginal, transdermal).
- Progestogen-only hormonal birth control associated with inhibition of ovulation (oral, injectable, implantable).
- Intrauterine device (IUD) and intrauterine hormone-releasing system (IUS).
- Bilateral Tubal occlusion (blocking of the fallopian tubes).
- Vasectomy of sexual partner (proven effective by documented absence of sperm on the ejaculation).
- Complete sexual abstinence (not to have male-female vaginal sex). This is defined as being in line with the preferred and usual lifestyle of the patient. Periodic abstinence e.g. calendar, ovulation, symptothermal, post-ovulation methods; declaration of abstinence for the duration of exposure to study drug; and withdrawal are not acceptable.

As monoclonal antibodies can be secreted in milk, women must stop nursing once they receive study drug and up to 16 weeks after the last study drug administration.

4.3 TREATMENT COMPLIANCE

Administration of the trial medication will be done in the study centre under the supervision of the investigator or a designee. The measured plasma concentrations will provide additional confirmation of compliance.

5. ASSESSMENTS

5.1 ASSESSMENT OF EFFICACY

Efficacy will be assessed using standard criteria that have been used in numerous AD studies, including the Eczema Area and Severity Index (EASI), the scoring of atopic dermatitis (SCORAD), Investigator Global Assessment (IGA) [REDACTED]

EASI

The EASI scoring system is based on the psoriasis area and severity index (PASI) used routinely in patients with psoriasis to describe signs and severity of the disease. The principle of integrating disease extent and severity to describe disease led to the definition of the EASI [R18-2665]. The EASI score assesses the extent of disease at four body sites and measures four clinical signs: (1) erythema, (2) induration/papulation, (3) excoriation, and (4) lichenification, each on a scale of zero to three. The EASI score confers a maximum of 72 and evaluates two dimensions of AD: disease extent and clinical signs. The suggested severity strata for the EASI are as follows: 0 = clear; 0.1–1.0 = almost clear; 1.1–7.0 = mild; 7.1–21.0 = moderate; 21.1–50.0 = severe; 50.1–72.0 = very severe [R18-2851]. The EASI score does not assess symptoms like pruritus and sleep loss [R18-2670].

SCORAD

The SCORAD index will also be included in the clinical trials and has three elements: extent of disease, disease severity and subjective symptoms. These combine to give a maximum possible score of 103. The commonly used SCORAD strata to classify AD severity are mild = 0–25, moderate = 26–50 and severe = 51–103 [R18-2664, R18-2679].

IGA

The IGA scale allows investigators to assess overall disease severity at one given time point, and it consists of a five-point severity scale from clear to very severe disease (0= clear, 1=almost clear, 2 = mild disease, 3 = moderate disease, 4= severe disease). The IGA scale uses clinical characteristics of erythema, infiltration, papulation, oozing and crusting as guidelines for the overall severity assessment [R18-2670].

[REDACTED]

